- 7.2.15 Use of any immunomodulatory agents within 30 days prior to study enrollment or planned use during the trial. Influenza vaccination or other routine vaccines will be permitted 30 days or more prior to administration of study medication

- 7.2.16 Active drug or alcohol use or dependence that, in the opinion of the sponsor, would interfere with adherence to study requirements.
- 7.2.17 Any surgical or medical condition which might significantly alter the absorption, distribution, metabolism, or excretion of drugs, or which may jeopardize the participant in the study. The Investigator should make this determination in consideration of the participant's medical history and/or clinical or laboratory evidence of any of the following:
- Inflammatory bowel disease
  - Major gastrointestinal tract surgery such as gastrectomy or gastroenterostomy
  - Pancreatic insufficiency
- 7.2.18 Use of HIV protease inhibitor or other strong or moderately strong CYP3A4 inhibitors:
- Strong inhibitors of CYP3A4 include: boceprevir clarithromycin, cobicistat, conivaptan, indinavir, itraconazole, ketoconazole, fluconazole, lopinavir/ritonavir, mibefradil, nefazodone, nelfinavir, posaconazole, ritonavir, saquinavir, telaprevir, telithromycin, voriconazole, aprepitant, grapefruit juice.
- Moderate inhibitors of CYP3A4 include: amprenavir, aprepitant, atazanavir, darunavir/ritonavir, diltiazem, erythromycin, fluconazole, fosamprenavir, imatinib, verapamil.
- Co-medication with weak inhibitors of CYP3A4 will be permitted. Weak inhibitors of CYP3A4 include: alprazolam, amlodipine, atorvastatin and other statins, bicalutamide, cilostazol, cimetidine, cyclosporine, fluoxetine, fluvoxamine, ginkgo, goldenseal, isoniazid, nilotinib, oral contraceptives, ranitidine, ranolazine, zileuton.
- Note: Use of azithromycin, regular orange juice and dihydropyridine calcium channel blockers (e.g. amlodipine, felodipine, nifedipine) are allowed.
- 7.2.19 Since panobinostat is a weak inhibitor of CYP2D6, participants using pharmaceuticals that are CYP2D6 substrates with a narrow therapeutic window are not permitted. Such agents are: thioridazine, tamoxifen, and the antiarrhythmics mexiletin, propafenone and flecainide. Drugs that are CYP2D6 substrates with a large therapeutic index such as certain anti-emetics, anti-hypertensives, and anti-depressants are generally safe to be co-administered with panobinostat.

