- 7.2.20 Participant has a history of anaphylaxis, allergy or serious adverse reactions to Interferon- $\alpha$ 2a/Interferon- $\alpha$ 2b or panobinostat.
- 7.2.21 Participant taking any of the following medications at the time of study entry: systemic steroids (inhaled or nasal steroid therapy or low dose oral steroid treatment up to no more than 7.5mg of Prednisone per day or the equivalent dose of alternative corticosteroids are permitted), interleukins, systemic interferons or systemic chemotherapy.
- 7.2.22 Regular use of concomitant medication with a known potential to lead to QTc prolongation or Torsades de pointes. These drugs include: quinidine, procainamide, disopyramide or any other class IA antiarrhythmic drug, sotalol, cisapride, amiodarone, bretylium, disopyramide, dofetilide, ibutilide or any other class III antiarrhythmic drug, macrolide antibiotics (clarithromycin, erythromycin, telithromycin), thioridazine, mesoridazine, chlorpromazine, pimozide, halofantrine, chloroquine, pentamidine, astemizole, arsenic trioxide, bepridil, domperidone, methadone, droperidol, levomethadyl. This list of medications was developed in collaboration with an external cardiology consultant, and represents those medications which are deemed to have an unacceptable risk of co-administration with panobinostat.
- Note: azithromycin, ciprofloxacin, levofloxacin and moxifloxacin are allowed.

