### 7.4 Study participant replacement

In stage 1 and 2, up to two participants dropping out of the study prior to study completion will be replaced by a new study subject. If, however, the subjects discontinue the study due to safety or tolerability concerns, the subjects will not be replaced. In stage 1, 2 and 3, all participants dropping out of the study prior to initiation of the first dose of the study medication will be replaced.

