### 8.6 Concomitant Medication

#### 8.6.1 Prohibited Medications

Participants will be excluded from the study if they are taking any of these medications during the course of this clinical trial:

- Systemic steroids up to 7.5 mg of Prednisone per day (or equivalent dose of alternative steroids); inhaled or nasal steroid therapy is also permitted
- Interleukins
- Systemic interferons other than the study medications
- Systemic chemotherapy
- Ritonavir, cobicistat or other similarly potent inhibitor of CYP3A4
- Grapefruit juice is a moderate to strong CYP3A inhibitor and may increase absorption and exposure to panobinostat. Therefore, participants will be instructed not to consume grapefruit juice during the study
- Pharmaceuticals that are strong or moderately strong CYP3A4 inhibitors, or CYP2D6 substrates with a narrow therapeutic window (see section 7.2.18 and 7.2.19)
- Drugs with a known potential to lead to QTc prolongation (see section 7.2.22)

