#### 8.6.4 Other concomitant medication

Any other current medical therapy either recorded at study entry or initiated during the study will be recorded in the CRF. Initiation of medical therapy that requires use of a drug specified in the exclusion criteria will result in withdrawal from the investigational drug. Medication entries should be specific to

trade name, the single dose and unit, the frequency and route of administration, the start and discontinuation date, and the reason for therapy.

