### 14.3 Sample Size Considerations

The primary efficacy analysis will compare changes from baseline to post-treatment HIV-1 DNA changes between the randomized treatment arms in stage 3. Allowing for one unevaluable participant in each arm due to lost to follow-up, ART discontinuation and/or other reasons, and under the assumption that a common standard deviation of change (measured as difference of log10 transformed HIV-1 DNA copies/million CD4 T cells) in all treatment arms is 0.436 (derived from baseline to end-of-study change in

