### 14.4.3 Statistical analysis of virological and immunological data

The primary efficacy endpoint is the change from baseline to day 10 in the number of HIV-1 infected CD4 T cells, as assessed by proviral CD4 T cell-associated HIV-1 DNA levels determined on a log-scale. The null hypothesis of no difference in the primary efficacy endpoint between the randomized treatments will be tested using a one-sided Wilcoxon rank sum test. The null hypothesis will be rejected with a  $p < 0.05$ .

Changes in the frequency of HIV-1-infected CD4 T cells (determined by levels of CD4 T cell-associated proviral HIV-1 DNA) from baseline to completion of the treatment phase will also be summarized as secondary efficacy endpoints and compared between the two randomized treatments. Mean and quartile plots will be used to summarize these efficacy endpoints at each visit. If feasible with the modest sample size, longitudinal data methods will also be used to evaluate and estimate treatment effects.

Analysis for the primary efficacy endpoint will use a modified intent-to-treat analysis, limiting to participants who have received at least one dose of randomized treatment and have data at baseline and day 10. Participants who go off ART, experience virologic failure or discontinue study participation for other reasons will be excluded from the efficacy analysis. For this analysis, mixed models with repeated measures will be considered (MMRM). Missing data will be managed using guidelines defined by the National Research Council.

Primary safety endpoints will be tabulated by Cohorts and randomized treatments.

Analyses of secondary virologic and immunologic outcomes will parallel the primary analyses outline above.

Baseline immunologic and virologic parameters will be assessed at multiple pre-entry timepoints (see Table 1). For analysis of primary and secondary endpoints, the mean of multiple baseline assessments will be used.

Secondary analyses of all immunologic and virologic parameters stratified by genetic polymorphisms (in HLA and IL-28B genes) will also be carried out.

Associations between changes in the various virologic and immunologic measurements will be evaluated using scatterplots and correlation coefficients.

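### Section 8.6.1 is mis-worded: read literally, it prohibits the low steroid dose that 7.2.21 permits at entry and lists no higher dose

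*Combined protocol and SAP*

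**What the plan says.** Section 8.6.1, on prohibited medications, opens with its consequence: "Participants will be excluded from the study if they are taking any of these medications during the course of this clinical trial". The first item on the list is "Systemic steroids up to 7.5 mg of Prednisone per day (or equivalent dose of alternative steroids); inhaled or nasal steroid therapy is also permitted".

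Exclusion criterion 7.2.21 bars systemic steroids at study entry, but with an exception. Inhaled and nasal steroids are allowed, and so is oral treatment at a low dose: "low dose oral steroid treatment up to no more than 7.5mg of Prednisone per day or the equivalent dose of alternative corticosteroids are permitted".

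Two other provisions bear on steroid use during the study. Section 8.6.4 states: "Initiation of medical therapy that requires use of a drug specified in the exclusion criteria will result in withdrawal from the investigational drug". Exclusion criterion 7.2.15 covers "Use of any immunomodulatory agents within 30 days prior to study enrollment or planned use during the trial"; it does not name steroids.

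**The concern.** The two rules use the same threshold, 7.5 mg of prednisone daily or equivalent, and point in opposite directions. At entry, doses at or below it are acceptable. On study, doses up to it are listed as prohibited, and doses above it are not listed at all.

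This is an operative list that site staff must apply, and its stated consequence is exclusion from the study, not merely a pause in dosing. A member of staff who followed the text as written would exclude a participant who had been correctly enrolled under 7.2.21. The same person would find nothing in 8.6.1 to act on if a participant were given a much higher systemic dose, which is the exposure a trial of immune activation has most reason to avoid.

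**Working it through.** No arithmetic applies: the question involves no sample size, error rate or event rate. The check is to take each kind of steroid use and see what each provision does with it.

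| Steroid use | 7.2.21 (at entry) | 8.6.1, read literally | 8.6.4 |
|---|---|---|---|
| Inhaled or nasal | Allowed | Allowed | Not triggered |
| Already on oral treatment, at or below 7.5 mg daily | Allowed | Excluded from study | Not triggered: nothing is started |
| Starts oral treatment on study, at or below 7.5 mg daily | Dose would have been allowed | Excluded from study | Not triggered: the dose falls within the 7.2.21 exception |
| Starts systemic treatment on study, above 7.5 mg daily | Dose would have been barred | Not listed | Withdrawn from study drug |
| Already on an allowed low dose, raised above 7.5 mg daily | Higher dose would have been barred | Higher dose not listed | Unclear: no new therapy is begun |

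1. **The contradiction.** Rows two and three show it. The literal on-study rule excludes exactly the oral dose range that the entry rule accepts.

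2. **The likely intent.** The bullet closes by saying that inhaled or nasal steroids are *also* allowed. That word makes sense only if the clause before it was a permission too. Restoring *except* before the dose limit makes the sentence coherent and brings it into line with 7.2.21. The item is a complete sentence in the current body text and shows no sign of a redaction or a broken table.

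3. **The higher doses.** Row four is covered elsewhere. Section 8.6.4 refers to drugs named in the exclusion criteria, and 7.2.21 names systemic steroids beyond its exception, so starting such treatment leads to withdrawal from study drug. Row five is less certain, because 8.6.4 speaks of initiating a therapy, and raising the dose of an existing one may not count. The two sections also carry different consequences: 8.6.4 ends study drug, whereas 8.6.1 ends study participation. Criterion 7.2.15 is not needed for row four and, since it does not name steroids, does not settle row five.

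4. **When a literal reading would take effect.** A medication history is taken at screening (9.2.1), concomitant medications are reviewed at V1 (9.3.2), and they are reviewed again on day 0, where the review is listed ahead of randomization and dosing (9.3.3). A participant in row two would therefore normally be noticed before the first dose. Section 7.4 provides that, in all three stages, "all participants dropping out of the study prior to initiation of the first dose of the study medication will be replaced".

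5. **What is left.** The remaining exposure is row three: someone who starts a low dose after day 0, together with staff who apply the bullet against its own closing words. Exclusion at that point could cost data, because under 14.4.3 "Participants who go off ART, experience virologic failure or discontinue study participation for other reasons will be excluded from the efficacy analysis", and stage 3 has no replacement after the first dose. The documents give no rate of steroid use, so the frequency cannot be stated.

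**The case against.** The strongest reply is that nobody would be misled. The bullet contradicts itself in a way that reveals its meaning, 7.2.21 states the intended rule clearly, and 8.6.4 already deals with starting higher doses. Most of this stands, and it is why the point sits at the lowest severity. It does not make the text correct: 8.6.1 is the list consulted during the study, and an inferable intent is a weaker safeguard than a correct sentence.

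Two stronger readings are tempting, and the documents support neither.

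- A reader might infer that 8.6.1 permits high-dose systemic steroids on study. It does not. Absence from one list is not permission, and 8.6.4 read with 7.2.21 withdraws study drug from a participant who starts them. The gap is limited to the wording of 8.6.1 and to the unclear case of a dose increase.
- A reader might infer a loss of evaluable participants, and so of power, in the small stage 3 single-agent arms. Section 14.3 plans for some loss ("Allowing for one unevaluable participant in each arm due to lost to follow-up, ART discontinuation and/or other reasons"), and one can calculate what a further loss would do. That calculation would be identical for a dropout of any cause, so it does not measure this defect. No steroid-use rate is given, and the participants most plainly caught by the wording would normally be identified before dosing and replaced.

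Nor should the item be read as a deliberate choice to ban low doses and tolerate high ones. Nothing in the protocol gives a reason for such a rule.

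**Conclusion.** Section 8.6.1 is wrong as written. Read literally, it prohibits the oral steroid dose that 7.2.21 allows at entry, and it lists no higher dose. This is an internal inconsistency caused by a dropped word, not a design choice, and its severity is the lowest.

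The contradiction follows from the two texts alone and is held with high confidence. The judgement that its effect is small rests on three readings: that the medication reviews at screening and on day 0 are carried out as described, that pre-dose dropouts are replaced under 7.4, and that 8.6.4 is applied to systemic steroids beyond the 7.2.21 exception. No effect on sample size, error rate or power is claimed, and no participant is assumed to be lost.

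**What to change.** Replace the first item in 8.6.1 with wording to this effect: *Systemic steroids, except oral treatment at no more than 7.5 mg of prednisone daily or an equivalent corticosteroid dose; inhaled and nasal steroids are also allowed.* This follows 7.2.21, including its limit to oral treatment, and brings a dose increase above the threshold expressly within the list.

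The cost is one line of protocol text at the next amendment, with no change to endpoints, sample size or analysis. There is one small downside. A participant who goes above 7.5 mg daily after dosing would be expressly excluded from the study and, in stage 3, not replaced. How often that would happen is unknown.

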#### 8.6.2 Required Medication

Participants are required to maintain a fully suppressive ART regimen (defined above) throughout entire study period. These medications will not be provided by the study. ART that includes a protease inhibitor or cobicistat is not permitted.

#### 8.6.3 Changes in cART Therapy

Changes in ART will be allowed for toxicity so long as a protease inhibitor or cobicistat is not included in the new regimen. These changes should be discussed with the study co-chairs. See Section 11.8 for procedures to be followed in case of virological failure.

#### 8.6.4 Other concomitant medication

Any other current medical therapy either recorded at study entry or initiated during the study will be recorded in the CRF. Initiation of medical therapy that requires use of a drug specified in the exclusion criteria will result in withdrawal from the investigational drug. Medication entries should be specific to

trade name, the single dose and unit, the frequency and route of administration, the start and discontinuation date, and the reason for therapy.

## **9.0 CLINICAL AND LABORATORY EVALUATIONS**

### **9.1 Study Conduct**

#### **9.1.1 Ethics and Regulatory Considerations**

The study will be conducted according to Good Clinical Practice (GCP) as specified in the ICH guidelines. The Sponsor will ensure that this study is conducted in agreement with all applicable laws, regulations and relevant ethics of Massachusetts General Hospital, Harvard Medical School, the City of Boston, the Commonwealth of Massachusetts and the United States.

#### **9.1.2 Informed Consent**

Informed consent will be obtained prior to the performance of any study procedures (including blood tests). The responsible investigator physician will review the consent with the patient. Consent will be documented by dated signatures of the patient, and the person obtaining consent. The informed consent will include all standard elements including, at a minimum, description of the study goals, entry criteria, details of the study, known risks of the therapy, participant's rights and criteria for record review by outside agencies (FDA for example). No elements of the informed consent will be waived. Only a fully IRB-approved consent will be used.

### **9.2 Definition of clinical evaluations**

#### **9.2.1 Medical history**

A medical history will be taken at the screening visit and should summarize all previous diagnoses, any allergies and a detailed medication history, including the start and stop dates of any antiretroviral medication (estimated if the exact dates cannot be obtained), and any immune-based therapies. A complete list of all prescription, non-prescription and alternative medications taken within 30 days prior to study entry with start and stop dates will also be recorded.

#### **9.2.2 Clinical assessment and complete physical exam**

Complete physical exam is required at baseline and includes examination of the eye (with retinal photographs), skin, head, mouth, neck; auscultation of the chest, cardiac exam; abdominal exam and exam of extremities. The clinical assessment will also include signs and symptoms, diagnoses, height, weight and vital signs (temperature, blood pressure, pulse).

#### **9.2.3 Targeted Physical exam**

A targeted physical examination will be driven by any signs and symptoms previously identified or new that the participant has experienced since the last visit. If indicated based on the participant's symptoms and history, evaluation for suicidal ideation will be performed using the Columbia Suicide Severity Rating Scale (available at <http://www.cssrs.columbia.edu/>).

#### **9.2.4 Pre-treatment assessments**

Pre-treatment assessments will be performed on the first day of the treatment week, prior to administration of the investigational drugs. Pre-treatment assessments on these days will include:

- ECG: QTc time must be <450msec for men and <470msec for women.
- Vital signs: Systolic blood pressure must be between 90-150 mm Hg, diastolic blood pressure must be between 65-100 mm Hg, heart rate must be between 50-100 bpm. Oral temperature measured according to standard procedures must be lower than 100.5F.

- Pregnancy test (urine HCG test, only in women of childbearing potential): Results must be negative.
- Lab tests: Most recent safety lab tests must be within the following limits:
  - a. Hemoglobin  $\geq 12.0$  g/dL for men and  $\geq 11.0$  g/dL for women
  - b. Absolute neutrophil count  $\geq 1500$  cells/mm^3
  - c. Platelet count  $\geq 150,000$ /mm^3
  - d. Creatinine level  $< 1.1 \times$  ULN
  - e. Total serum bilirubin  $< 1.1 \times$  ULN
  - f. AST (SGOT) and ALT (SGPT)  $< 1.1 \times$  ULN
  - g. Mg, K  $>$  LLN. If the value is  $<$  LLN, then the patient's potassium or magnesium should be supplemented following the availability of that laboratory result. Patients must then undergo a repeat biochemistry test to demonstrate values  $\geq$  LLN. These values must be  $\geq$  LLN before the patient is dosed with oral panobinostat.
- Targeted physical exam: Targeted physical must not reveal new signs of organ dysfunction or acute illness.
- Eye exams will be performed using an ophthalmoscope (Welch Allyn, PanOptic Ophthalmoscope) and retinal photographs will be taken from each eye and electronically documented. These fundoscopic exams will be non-mydriatic.

If any of these criteria are not met, study medication must not be given. Delay of the study drug administration for up to two weeks until all criteria are met is possible if permitted by the study chairs.

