- 7.1.10 Laboratory values at screening visit that meet the following criteria:
  - a. Hemoglobin  $\geq$  12.0 g/dL for men and  $\geq$  11.0 g/dL for women
  - b. Absolute neutrophil count  $\geq$  1500 cells/mm^3
  - c. Platelet count  $\geq$  150,000/mm^3

- d. Prothrombin time (PT) < 1.1 x upper limit of normal (ULN) and partial thromboplastin time (PTT) < 1.1 x ULN
  - e. Creatinine level < 1.1 x ULN
  - f. Total serum bilirubin < 1.1 x ULN
  - g. AST (SGOT) and ALT (SGPT) < 1.1 x ULN
- 7.1.11 Normal TSH. If K and Mg levels are below the limits of normal, participants will be provided with supplements and their levels will be rechecked. Supplementations will continue until electrolyte levels are normalized.
- 7.1.12 Negative serologic test for HBsAg.
- 7.1.13 Negative serologic test for antibodies to HCV or negative HCV PCR if anti-HCV antibodies are positive.
- 7.1.14 QTc interval in an ECG performed at the screening visit must be <450msec for men and <470msec for women.
- 7.1.15 A negative T spot TB test or a negative PPD skin test within the last 24 months. Participants with positive assays may participate if they have completed a recommended treatment course for latent TB in the past.
- 7.1.16 Participants should have received vaccination for pneumococcal disease within the last 5 years. Participants may still be enrolled in case there is a medical or personal contraindication against pneumococcal vaccination.
- 7.1.17 No evidence of clinical coronary heart disease, as determined by a stress echocardiogram, conducted within 2 years prior to study initiation. Data from a non-imaging exercise stress test or a nuclear imaging stress test conducted within two years prior to study initiation are also acceptable. However, when stress tests without imaging were done, a resting echocardiogram should be performed prior to enrollment to assess the cardiac ejection fraction. Patients who are unable, or predicted to be unable, to achieve >85% of their maximal predicted heart rate will undergo a dobutamine stress echocardiography instead of an exercise stress echocardiography since an exercise stress test would be insufficiently sensitive in this case. The stress test will be conducted at the Massachusetts General Hospital Cardiology division. [name], the protocol cardiologist, will facilitate short-term scheduling of patients.

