### 9.3 Schedule of Events

#### 9.3.1 Overview

The study will comprise three phases:

1. A pre-treatment screening/observation phase
2. A treatment phase of 1 week with panobinostat only (Arm A), pegylated IFN- $\alpha$ 2a only (Arm C) or the combination of panobinostat and pegylated IFN- $\alpha$ 2a (Arm B).
3. A post-treatment observation period of three weeks.

A graphical overview of the study is given in Figure 1. A summary of all study procedures at each visit is provided in Table 1. Time windows and blood draws for each study visit are also listed in Table 1.

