Pregnancy testing 	X	X	X					X
Hep B/C serologies, PPD/TB Spot PT, PTT	X							
Eye exam	X		X					
Stress echocardiogram/dobutamine stress test	X							
HIV antibody	X							
Differential blood count and CD4/CD8 T cell counts	X	X	X			X	X	X
Plasma HIV-1 RNA	X		X	X		X	X	X
Complete/targeted physical exam	X	X	X			X	X	X
Panobinostat PK			X	X		X	X	
ECG	X		X	X		X		
Histone acetylation levels		X	X	X		X	X	X
HIV-1 DNA		X	X			X	X	X
Viral outgrowth assays		X					X	
CD4 T cell -associated HIV-1 RNA		X	X	X		X	X	X
HIV-1 DNA in CD4 T cell subsets		X					X	
Immune phenotyping		X	X	X		X	X	X
Functional immune assays		X		X		X	X	
Gene expression profiling		X					X	

Immune activation markers		X		X		X	X	

Table 1: Schedule of events during the study. (*blood draws on this day will occur 6h after administration of study drug). CBC includes WBC, RBC, PLT, Hgb, Hct, MCV, MCH, RDW, MCHC, MPV. Liver function tests include AST/ALT, TBili, DBili, Albumin. Chemistry levels include Na, K, Cl, HCO3, BUN, Crea, Glucose, Mg. Women of childbearing potential only. †Number reflects time interval during which study visit should occur from Study Entry.
								

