### 9.3.3 Treatment phase

Study entry will be defined as the day on which the first dose of study drug is administered (day=0, visit V3).

On this day, participants will have the following procedures performed:

- Perform a pregnancy test, ECG and vital signs/physical exam (including eye exam), as described in pre-treatment assessment (9.2.4).
- Review concomitant medications.
- Collect blood for baseline immunologic and virologic assays.
- Perform randomization to treatment Arm A or B or C.
- After the above procedures are completed, administer one s.c. dose of PEG-IFN- $\alpha$ 2a in patients randomized to treatment Arm B and C.
- Immediately after the first administration of PEG-IFN- $\alpha$ 2a, participants will be asked to take the first pill of panobinostat p.o., at the stage-specific dose if randomized to arm A or B.
- At 6h after administration of panobinostat, blood samples will be collected for virological, immunological and pharmacokinetic assays.
- 4-6 hours after administration of panobinostat, at the time of Cmax for panobinostat, a 12-lead ECG will be performed.
- On discharge, participants randomized to stage A or B will receive two more stage-specific panobinostat doses and will be instructed to take them in the mornings of study day 2 and day 4.

On Day 2, participants will be called by phone by one of the study investigators to discuss possible side effects. Participants will return on Day 4, six hours after administration of the third dose of panobinostat (visit V4), for collection of blood samples for virological, immunological and gene expression studies, as described in Table 1, and for an ECG. The full volume of blood to be collected on day 4 will only be collected if the most recently available hemoglobin level is  $\geq 12.0$  g/dL for men and hemoglobin  $\geq 11.0$  g/dL for women.

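### The pre-dose liver limit has no scheduled result newer than screening, and no liver test is scheduled between day 4 and day 28

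*Combined protocol and SAP*

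**What the plan says.** Section 9.2.4 sets laboratory limits that must be satisfied before the first dose: "Most recent safety lab tests must be within the following limits". It does not itself order a new sample. If any limit is missed, drug must be withheld, although "Delay of the study drug administration for up to two weeks until all criteria are met is possible" with the study chairs' agreement. The liver limits match those for eligibility: criterion 7.1.10 requires "AST (SGOT) and ALT (SGPT) < 1.1 x ULN" and the same multiple for total bilirubin.

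Timing comes from the schedule of events. Section 9.3.1 states that "A summary of all study procedures at each visit is provided in Table 1". The table has separate rows for liver function and chemistry. Footnote 2 reads "Liver function tests include AST/ALT, TBili, DBili, Albumin". Footnote 3 defines chemistry as electrolytes and bicarbonate together with "BUN, Crea, Glucose, Mg", so it contains no liver analyte. The neutrophil count comes from the row "Differential blood count and CD4/CD8 T cell counts". The V1 and V2 intervals are counted back from study entry, and 9.3.3 says "Study entry will be defined as the day on which the first dose of study drug is administered".

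**The concern.** A pre-dose limit on the latest result protects participants only if a result newer than the eligibility result can exist. For hemoglobin, neutrophils, platelets, creatinine, potassium and magnesium the schedule provides one. For AST, ALT and bilirubin it does not, so the scheduled liver check cannot fail in anyone who was eligible.

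The gate carries extra weight here because the only scheduled on-treatment liver sample is taken on day 4, six hours after the third and last panobinostat dose. The Table 2 instruction to discontinue dosing for liver abnormalities therefore cannot be triggered by a scheduled result while a planned dose remains.

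After dosing, 10.9 bases escalation to 10 mg and 15 mg on related grade 3 or higher events up to Day 28. Section 7.3 lets stage 1 and 2 participants enter stage 3 only if they had no clinical or laboratory grade 3 or 4 event. A liver rise that begins after day 4 and settles before day 28 would inform either decision only if symptoms or the day 10 examination prompted an unscheduled test.

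**Working it through.** No stated figure in the plan needs reproducing. The check is a mapping of the Table 1 rows to visits, followed by day differences.

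| Table 1 row | V1 | V2 | D0 | D4 | D10 | D28 |
|---|---|---|---|---|---|---|
| Liver function | X | | | X | | X |
| Chemistry | X | X | | X | X | X |
| CBC | X | X | X | X | X | X |
| Differential | X | X | X | X | X | X |

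**Gate analytes (9.2.4).** Hemoglobin, neutrophils, platelets, creatinine, bilirubin, AST, ALT, magnesium and potassium make 9. Scheduled again after V1 and by first dose:
- hemoglobin, platelets (CBC) and neutrophils (differential) at V2 and D0;
- creatinine, potassium and magnesium (chemistry) at V2.

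That is 3 + 3 = 6. Not scheduled again: 9 - 6 = 3, namely AST, ALT and bilirubin.

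**Age of the scheduled liver value at first dose.** V1 is at most 30 days before study entry and V2 at most 10. The maximum age is 30 days now and would be 10 with a liver test at V2.

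**Post-dose gap.** With the Table 1 windows, D4 is day 4 to 5, D10 is day 8 to 12 and D28 is day 26 to 30.
- Now, D4 to D28: 28 - 4 = 24 days; shortest 26 - 5 = 21, longest 30 - 4 = 26.
- With D10 added, D4 to D10: 10 - 4 = 6 days; shortest 8 - 5 = 3, longest 12 - 4 = 8.
- With D10 added, D10 to D28: 28 - 10 = 18 days; shortest 26 - 12 = 14, longest 30 - 8 = 22.

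Scheduled post-dose liver results up to Day 28 go from 2 to 3.

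**Assay count for the fix.** 3 analytes x 2 visits = 6 per participant; 6 x 34 = 204.

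**The case against.** The strongest reply is that 13.2.2 lists ALT, AST and total bilirubin under chemistry. If that list defined the Table 1 chemistry row, liver values would exist at V2 and D10 and both parts of this point would fail. The mismatch is real, but it does not carry the argument:
- Section 13.2 leaves timing to Table 1, where the chemistry row has its own footnote and liver tests have a separate row that would otherwise be redundant.
- Section 13.2.3 likewise lists PT and PTT under hematology, yet Table 1 draws them only at screening.
- The 13.2.2 list omits magnesium and glucose, which footnote 3 includes, so it is not a definition of that row.

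Other objections stand in part. No study drug is given between V1 and day 0. Entry excludes hepatitis B, active hepatitis C and past conditions linked to chronic liver disease, and requires a stable ART regimen for 12 weeks. The targeted examination or an unscheduled test can still stop dosing. The safety summaries in section 5 name no hepatic events. A day 10 result cannot stop dosing. Under 11.7 only findings judged clinically significant become adverse events, and 10.9(a) lets the SMC allow progression when grade 3 events are clinically insignificant laboratory abnormalities. Section 10.9(b), for grade 4 and above, has no such allowance. These points limit the consequence; they do not supply a current liver value.

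A two-week delay could suggest a value up to 30 + 14 = 44 days old. That holds only if the delay is added to the V1 interval. Because study entry is the day of first dose, 30 days is the limit as written.

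**Conclusion.** The point holds for scheduled tests. Three of the nine gate analytes have no scheduled result after screening, so the liver limit in 9.2.4 repeats the eligibility check on a value up to 30 days old. After dosing there is a nominal 24-day interval with no scheduled liver result inside the period used for escalation decisions.

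This rests on reading Table 1 with its footnotes as the governing schedule. How many participants would be affected cannot be estimated, because the documents give no liver event rate at these doses. The one-week co-primary safety window is not affected. This is a cheap safety improvement that should be made, and it does not invalidate the design.

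**What to change.** 1. In Table 1, mark the liver row at V2 and D10, for at least AST, ALT and total bilirubin. Leave footnote 3 as it is. The liver and chemistry rows would then share the same visits (V1, V2, D4, D10, D28), so the wording difference in 13.2.2 would no longer affect timing.
2. In 9.2.4, keep the rule that the latest result counts, and add that the liver result must be from V2 or later. Any later repeat or unscheduled result, normal or abnormal, then takes precedence, which fits the permitted delay.
3. Keep the numerical limits and the Table 2 liver actions.

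The cost is two table entries, one clause and about 204 assays in total. No new visit or draw is needed, assuming the chemistry sample already taken at each visit is sufficient; the documents give no tube details. A participant at or above 1.1 x ULN at V2 may be delayed or not dosed, and day 10 may reveal transient rises that need grading. Neither number can be estimated from the documents.

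The change leaves 14 to 22 days without a scheduled liver test between D10 and D28, and it does not make Table 2 liver stopping act before the last planned dose.
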